APPENDIX C: PDA MODULE/CASE REPORTING FORM (CRF)

CLINICAL PRE-CATHETERIZATION DATA (To be obtained within 2 weeks of the procedure)
Patient ID:
Date of Birth:// MM /DD/YYYY
Date of Clinical Assessment:// MM /DD/YYYY
Sex: Male Female
Ethnicity: White African American or Black Hispanic or Latino Asian
Pacific Islander 🔲 Native American 💭 Other 🔲
Current weight:kg Birth weight:kg
Height: cm
Gestational age at birth: weeks
Other associated congenital heart defects: Left-to-right shunt lesions Right-to-left shunt lesions Other (Specify)
Other associated co-morbidities: (Mark all that are present) Pulmonary hypertension Necrotizing enterocolitis Grade Current Resolved Intraventricular hemorrhage Grade Retinopathy of prematurity Chronic lung disease Renal insufficiency History of sepsis Other (Specific)
Genetic syndrome:
Ongoing medical support: Mechanical respiratory support Supplemental oxygen
Conventional Ventilator 🔲 Oscillator 🔲 Non-inavasive 🔲 CPAP 🛑
Nasal Cannula 💭 None 🔲
Inotropic support
1

Estimates of pulmonary hypertension: Tricuspid Regurgitation:m/s Right ventricular pressure estimate (+RA):		
Interventricular septal flattening in systole: Normal septal curvature Mild septal flattening Moderate septal flattening Ventricular septal inversion		
Left ventricular ejection fraction:%		
Other echo findings: Left aortic arch 🥏 Right aortic arch 💭 Unknown arch sidedness 🥃		
Abdominal aorta diastolic flow reversal Coarctation of aorta		
Ventricular septal defect 💭 Atrial septal defect 💭 Pericardial effusion 💭		
Mitral Valve Regurgitation: None/Trivial 🔲 Mild 🔲 Moderate 🔲 Severe 🔲		
Tricuspid Valve Regurgitation: None/Trivial 🔲 Mild 🔲 Moderate 🔲 Severe 🔲		
Pulmonary Valve Regurgitation: None/Trivial 🔲 Mild 🔲 Moderate 🔲 Severe 🔲		
Other congenital heart defects (Specify)		

CATHETERIZATION DATA
Date of Catheterization:// MM / DD / YYYY
Weight:
Indication for PDA closure: Left heart enlargement Pulmonary hypertension Prematurity SBE prevention Frequent respiratory infection Failure to thrive Ventilator dependence Other (Specify)
Pre-Procedure Respiratory Severity Score (Mean airway pressure x FiO ₂):
Anesthesia: General endotracheal anesthesia Moderate sedation Monitored anesthesia care Was Patient Specifically Intubated for the Procedure Yes No
Guidance: Fluoroscopy only Trans-thoracic echo only Combination of Fluoroscopy and Echo
Location: Cardiac Cath Lab Bedside Other Location Started in another location but completed in the cath lab
Access: Venous access only 🔲 Arterial access only 🔲 Venous and arterial access 🔲
Right femoral vein 🔲 Left femoral vein 💭 Right femoral artery 🔲 Left femoral artery
Use of Ultrasound for vascular access: Ultrasound was primarily used for access Ultrasound was used after failed attempted access without ultrasound Ultrasound was not used for vascular access
Hemodynamics: Not performed
Qp:Qs Pulmonary artery pressure mmHg
Pulmonary vascular resistanceWU m ²
Largest venous sheath size: French Largest arterial sheath size: French
PDA Morphology

	P	atent	Ductus Arte	riosus Module		-
Type A (Conic				Type D Ty (Complex) (E	ype E e and a set of the set of 	Type F
Intra-Pro	cedure PDA me	asureme	nts:			
	If Angiographi were po	c measure erformed			were performed on ral trans-thoracic ec	
Aortic en	tic endmm Aortic endmm					
Pulmona	Pulmonary artery endmm Pulmonary artery endmm				mm	
Minimum luminal diametermm Minimum luminal diametermm				mm		
Length	Lengthmm Lengthmm					
Heparin	administration:	Yes 🔲	No	If Yes, highest A	CT secs	
Device d	elivery:	Antegr	ade 🔲	R	etrograde 🔲	
Contrast No contra	: ast was used		Total contras	t volume ml	L/kg	
Radiation Total Flue	n: oroscopy time: _		minutes			
Cumulati	ve DAP:					
DAP Unit	s: Gy-cm2 🔲	dGy-cm	2 CGy-cm2	mGy-cm2 m	icgGy-m2 🔲	
Device (s	;):					
Device count	Device			Device outcom	ne	
1		Implant	ted, not released	Implanted, released	Implanted, release	d, and retrieved
2		Implant	ted, not released	Implanted, released	Implanted, release	d, and retrieved
3		Implant	ted, not released	Implanted, released	Implanted, release	d, and retrieved

tue Antonioque Modulo Datant I

Implanted, not released

[figure not shown]
4

Implanted, released

Implanted, released, and retrieved

Implanted device # 1 size:mm Xmm Device type:
Implanted device # 2 size: mm Xmm Device type:
Implanted device # 3 size: mm Xmm Device type:
Implanted device # 4 size:mm Xmm Device type:
Residual shunting by angiography: Grade 0 (None) Grade 1 (Trivial) Grade 2 (Mild) Grade 3 (Moderate) Grade 4 (Severe)
Residual shunting by intra-procedural echo if utilized (Optional): Grade 0 (None) Grade 1 (Trivial) Grade 2 (Mild) Grade 3 (Moderate) Grade 4 (Severe)
Gradient across the proximal left pulmonary artery (Cath/Echo – Optional): Pre-procedure peak gradient Post-procedure peak gradient Post-procedure peak gradient Post-procedure mean gradient
Gradient across the distal aortic arch (Cath/Echo – Optional): Pre-procedure peak gradient Pre-procedure peak gradient Post-procedure peak gradient Post-procedure mean gradient
Other echo findings (optional):
Increased tricuspid regurgitation compared to baseline: Yes 🔲 No 🔲
Increased pulmonary valve regurgitation from baseline: Yes 🔲 No 🔲
Left ventricular ejection fraction: % Pericardial effusion: Yes 🔲 No 🦲
Other echo findings (Specify)
Date Patient Extubated Following Procedure:// MM / DD / YYYY
Date of Hospital Discharge:// MM DD YYYY
Adverse Events:
Where there any Adverse Events during the procedure: Yes No No (If Yes, complete the AE Form)

Patent Ductus Arteriosus Module

Confidential

Patent Ductus Arteriosus Module

Other echo findings:
Increased tricuspid regurgitation compared to baseline: Yes 🔲 No 🔲
Increased pulmonary valve regurgitation from baseline: Yes 🔲 No 🔲
Left ventricular ejection fraction: %
Pericardial effusion: Yes No
Evidence for Pulmonary Hypertension: Yes 🔲 No 🔲
Other echo findings (Specify)

FOLLOW-UP CHEST X-RAY (Optional)

Post-procedure chest X-Ray: Date/ MM / DD	/ YYYY
Cardiomegaly	Increased pulmonary vascular markings
Device malposition	on 🥅
Other C (Spec	ify)

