2.1 Primary Endpoint(s)

Safety Endpoint: Composite rate of major device- or procedure-related adverse events (AE) of interest through 6 months' post-implantation procedure. AEs of interest are broadly categorized as:

- a. Vascular access complications
- **b.** Valvular Injury
- **c.** Device embolization
- d. Pulmonary or aortic vessel stenosis

Access vessel complications include femoral arterial or femoral/jugular venous complications noted during the procedure, immediately after the procedure or delayed (>24 hours). They range from bleeding from access sites, arterial or venous thrombosis with or without the need for treatment to loss of limb secondary to arterial occlusion.

Valvular injury includes damage to the tricuspid valve or other cardiac valve resulting in immediate post-procedural valvular dysfunction.

Device embolization includes malposition of the device either during or after the procedure or delayed (>24 hours). The outcome of device embolization ranges from observation, transcatheter retrieval at time of procedure or at a separate time, surgical retrieval, other end organ damage, tomortality.

Adjacent vessel stenosis includes a narrowing of the aorta or the left pulmonary artery directly as a consequence of device implantation for PDA closure. Vessel stenosis could happen either during or after the procedure or delayed (>24 hours). The outcome of vessel stenosis ranges from no intervention needed to repeated transcatheter and surgical therapies.

For details of each AEs and definitions, refer to **Appendix A**.

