4.4 Post-Procedure Follow-up

The follow-up assessment must be obtained within 48-hoours, 1-month and 6-months after the procedure. The schedule of all assessments is provided in Appendix E. The following post-procedure follow-up assessments, diagnostic tests and evaluations and must be included in the PDA module:

- a. Demographics- including subject's age, weight
- b. Transthoracic echo (TTE) including checking for the presence of the device within the PDA, degree of residual shunting if any, spectral Doppler findings, estimates of pulmonary

hypertension, left ventricular function and dimensions, pulmonary and aortic flow and dimensions, pulmonic and tricuspid valve regurgitation

Subjects should be on appropriate endocarditis prophylaxis according to the American Heart Association recommendations for prophylaxis.

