6.3 Core Laboratory

A Core Lab will not be used to review and adjudicate patient's clinical information, angiograms and transthoracic echocardiography. However, the CCISC will randomly audit up to ten percent of the patients' data entered in the PDA module from each institution. Service details are previously outlined in the applicable Service Agreement between the CCISC participating site and the CCISC.

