7.5 Other Endpoints

The following endpoints will be summarized using descriptive statistics.

a. **Implant success:** The frequency and percentage of implant success (defined in Section 7.4) will be reported. This analysis will include all subjects entered in the PDA module.

- b. **PDA shunt status at follow-up visit**: The frequency and percentage of PDA shunt status at the 6 month follow-up visit, as assessed by the TEE, will be reported. Shunt sizes categories are: Grade 0/1, 2, and Grade 3/4. This analysis will include subjects who achieve a successful implant.
- c. **Obstruction measurements at follow-up visit**: The frequency and percentage of significant obstruction of the left pulmonary artery and the frequency and percentage of significant aortic obstruction (defined in Section 7.3) at the 6 month follow-up visit will be reported. Both analyses will include subjects who achieve a successful implant.
- d. **Major and Minor Complications**: The frequency and percentage of major and minor complications (refer to **Appendix A** for definition) from the time of the implant procedure will be reported.
- e. **Death**: The frequency and percentage of death will be reported.
- f. **Additional data**: Demographics and baseline characteristics, procedure information, left ventricular function and dimensions, pulmonic and tricuspid regurgitation, adverse events, subjects lost to follow-up will also be summarized.

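### The routine echo pages grade tricuspid and pulmonary regurgitation at baseline but not after implant, so the Section 7.5 summary can give no more than a proportion increased (minor)

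*Protocol*

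**What the plan says.** **Baseline.** The pre-catheterization echo page in Appendix C has a four-level item for each valve, beginning "Tricuspid Valve Regurgitation: None/Trivial" and "Pulmonary Valve Regurgitation: None/Trivial" and continuing through mild and moderate to severe.

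**After implant.** The optional procedural echo block and the later echo block each carry one item per valve: "Increased tricuspid regurgitation compared to baseline: Yes" (or No) and "Increased pulmonary valve regurgitation from baseline: Yes" (or No). A free-text line for other findings follows.

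**What the text asks for.** Section 4.4 lists "pulmonary and aortic flow and dimensions, pulmonic and tricuspid valve regurgitation" among the follow-up transthoracic echo content and names no scale. Appendix E schedules that echo within 48 hours, at 30 days and at 6 months. Section 7.5(f) says that "left ventricular function and dimensions, pulmonic and tricuspid regurgitation, adverse events, subjects lost to follow-up will also be summarized".

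**Valve injury.** Section 2.1 names it among the safety events of interest: "Valvular injury includes damage to the tricuspid valve or other cardiac valve resulting in immediate post-procedural valvular dysfunction". The Appendix D event form records the injured valve, the timing, the degree of regurgitation (mild, moderate, severe), the mechanism and the outcome.

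**The concern.** A planned summary should rest on fields that can be compared over time. Here the starting value is an ordered grade and the later value is a yes or no. An infant who goes from no regurgitation to mild and one who goes from none to severe receive the same tick.

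This is a matter of data capture, fixed in the protocol's own case report form. A statistical analysis plan can choose tables, but it cannot restore a grade that was never recorded.

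What is at stake is the usefulness of the descriptive regurgitation summary, and with it a targeted check on whether important new regurgitation was reported as an event. The routine echo is the record scheduled for every implanted infant, whereas the event form exists only where an investigator filed one.

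**Working it through.** No rate, sample size or interval depends on this point, and the protocol gives no regurgitation figures to reproduce. The check sets the forms side by side.

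**1. Levels recorded per valve**
- Baseline echo (Appendix C): 4 ordered grades.
- Procedural and later echo blocks (Appendix C): 2 values, increased Yes or No.
- Valve-injury section of the event form (Appendix D): 3 grades, only for a filed event.

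**2. What a tick can mean.** Assume that Yes means a rise of at least one full grade. The form does not say so.

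| Baseline grade | Follow-up grades behind Yes | Follow-up grades behind No |
|---|---|---|
| None/Trivial | Mild, Moderate, Severe (3) | None/Trivial (1) |
| Mild | Moderate, Severe (2) | None/Trivial, Mild (2) |
| Moderate | Severe (1) | None/Trivial, Mild, Moderate (3) |
| Severe | none (0) | all four (4) |

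The full shift table has 4 × 4 = 16 cells, of which 3 + 2 + 1 + 0 = 6 fall under Yes and 1 + 2 + 3 + 4 = 10 under No. The form can record 4 × 2 = 8 combinations, one of which is empty (Severe with Yes), leaving 7. Only 2 of those 7 fix the follow-up grade: None/Trivial with No, and Moderate with Yes.

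**3. Newly moderate or severe.** For an infant starting at None/Trivial, Yes mixes one grade below that threshold (Mild) with two at or above it. For an infant starting at Mild, Yes would imply moderate or severe, but only under the full-grade assumption. If a site ticks Yes for a smaller rise, such as none to trivial, which are a single baseline category, even that inference fails.

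**4. Improvement.** For every baseline grade above None/Trivial, No covers both unchanged and improved.

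**5. Whether another source supplies the grade**
- The event form does so for filed valve injuries. The visible prompt to complete it, on the procedure page, concerns events during the procedure. The later echo block shows no prompt from a Yes tick to that form.
- Section 6.3 states: "A Core Lab will not be used to review and adjudicate patient's clinical information, angiograms and transthoracic echocardiography". It provides instead for a random audit of up to ten percent of patients' data per institution.
- Under Section 6.4.2 the Clinical Events Committee reviews reportable adverse events, so an increase that was never filed is not routed to it.

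**6. Comparison within the module.** Residual shunt is graded 0 to 4 on the procedure page, so graded recording after implant is already accepted practice.

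**The case against.** The strongest reply is that severity is captured where it matters. Section 5.2 requires the event form for events caused by the procedure or device or seen at follow-up. Section 8.2 makes every potentially related event reportable whether or not it is serious, and also where relatedness is unknown. Clinically important new regurgitation should therefore reach the graded Appendix D form. **This stands.** What stays ungraded is an increase that the investigator does not regard as an adverse event, a narrow group and probably weighted towards mild change.

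Second, Section 7.5(f) promises a summary, not a shift table, and a proportion increased is a valid summary. **This also stands**: the protocol does not contradict itself. The point is that the form limits the summary more than it needs to.

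Third, any Yes without a valve-injury form can already be listed and the grade sought in source documents. **True**, so a check on under-reporting is possible now. It is less targeted, because mild and severe changes enter the same list.

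Two stronger readings are tempting, and the protocol supports neither:
- *A reader might infer that no severity of regurgitation is recorded anywhere after implant.* Appendix D records it by valve and timing for reported injuries.
- *A reader might infer that the primary safety endpoint is compromised, because valve injury is one of its categories.* Section 7.1 counts major adverse events, and Appendix A defines major by consequence (death, threat to life, lasting disability, major open surgery), not by regurgitation grade. The Yes/No item does not enter that rate.

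**Conclusion.** The point holds as a minor, inexpensive improvement confined to the routine echo pages and the descriptive summary in Section 7.5(f). As the forms stand, that summary can show how many infants were marked as increased. It cannot show the grade reached, cannot separate unchanged from improved, and cannot single out new moderate or severe regurgitation that was not filed as a valve injury. The primary safety rate is unaffected.

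The size cannot be expressed as a number of infants, since the protocol states no baseline distribution or expected rate of regurgitation. The count of 2 out of 7 combinations describes the form, not the patients, and rests on the full-grade reading of Yes.

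One caveat remains. The follow-up form is incomplete in the text available: follow-up fields that Section 4.4 requires, such as device presence and residual shunt, do not appear there. A graded regurgitation field elsewhere is unlikely, given the Yes/No items that do appear, but it cannot be excluded and should be checked against the full form first.

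**What to change.** 1. In Appendix C, replace the Yes/No items for the tricuspid and pulmonary valves on the follow-up echo pages with the four-level baseline scale. Do the same on the optional procedural echo block, for use where that echo is done.
2. In Section 7.5(f), report the shift from the baseline grade to the grade within 48 hours, at 30 days and at 6 months, among infants with an echo at that visit. State the number with an echo, and give the proportion newly moderate or severe.
3. List newly moderate or severe cases that have no valve-injury form, for a data query.

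**Cost.** A small CRF edit, one set of shift tables and a query listing. The follow-up echo is already scheduled and regurgitation is already part of it, so no extra test or reader is needed and no clinical rule changes. Infants already entered keep Yes/No unless sites take the grade from existing echo reports. The tables may also be incomplete: Sections 3.1 and 4 require no special follow-up testing for the study, and Section 8.1 allows missing echo details not to count as a deviation.

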APPENDIX D: ADVERSE EVENT REPORTING FORM

ADVERSE EVENT FORM

Type of adverse event:
Device embolization Access complications Vessel stenosis Valve injury Other
Device embolization:
During the procedure (In the cath lab): Yes 🔜 No 🔜
After the procedure (In recovery): Yes 🔜 No 🔜
Delayed embolization (>24 hours later): Yes 🦲 No 🦲
Embolization site:
Left pulmonary artery Right pulmonary artery
Aorta/systemic artery Right ventricle Other site (Specify)
Outcome of embolization:
Observation only
Successful transcatheter retrieval with PDA occlusion with another device
Successful transcatheter retrieval, PDA not occluded with another device
Successful transcatheter retrieval, PDA surgically ligated
Unsuccessful transcatheter retrieval, PDA occlusion with another device
Unsuccessful transcatheter retrieval, PDA not occluded with another device
Unsuccessful transcatheter retrieval, PDA surgically ligated
Device embolization led to initiation of inotropic suport
Device embolization led to initiation of mechanical circulatory support
Device embolization led to patient mortality
Access complications:
During the procedure (In the cath lab): Yes No
After the procedure (In recovery): Yes No
Delayed access complication (>24 hours later): Yes No
Arterial access complication:
Transient loss of pulse with spontaneous recovery without intervention
Transient loss of pulse with recovery following intervention
Non-occlusive arterial thrombus – No intervention needed/performed
Non-occlusive arterial thrombus – Requiring intervention
Occlusive arterial thrombus – Requiring intervention
Medical Surgical
Loss of limb secondary to vascular access complication
Venous thrombosis – anticoagulation/antiplatelet therapy performed
Venous thrombosis – anticoagulation/antiplatelet therapy not performed

Vessel stenosis:

Noted during the procedure (In the cath lab): Yes Noted after the procedure (In recovery): Yes Delayed finding (>24 hours later): Yes

No	
No	
No	

Left pulmonary artery stenosis:

No intervention was required Intervention performed during the same catheterization Intervention performed within 24 hours Intervention performed > 24 hours Re-intervention on the left pulmonary artery is unlikely Re-intervention on the left pulmonary artery is likely *Type of intervention for the left pulmonary artery stenosis*: Retrieval of device with no further intervention Retrieval of device with repositioning of the same device Retrieval of device with use of a different device Balloon angioplasty of the left pulmonary artery stenosis Surgical repair

Descending aorta stenosis:

No intervention was required Intervention performed during the same catheterization Intervention performed within 24 hours Intervention performed > 24 hours Re-intervention on the aorta is unlikely Re-intervention on the aorta is likely

Type of intervention for the descending aorta stenosis:

Retrieval of device with no further intervention Retrieval of device with repositioning of the same device Retrieval of device with use of a different device Balloon angioplasty of the descending aorta stenosis Stent implantation for descending aorta stenosis Surgical repair

Valve	e Injury:
	Noted during the procedure (In the cath lab): Yes No
	Noted after the procedure (In recovery): Yes 📃 No 🔜
	Delayed finding (>24 hours later): Yes No
Injure	ed Valve:
	Tricuspid valve
	Pulmonary valve
	Mitral valve
	Aortic valve
Degre	ee of regurgitation:
	Mild
	Moderate
	Severe
Mech	anism of regurgitation:
	Avulsion of chordae
	Avulsion of chordae Central non-coaptation of the valve Valve leaflet injury Injury to valve appulus
	Valve leaflet injury
	Injury to valve annulus
Outco	ome:
	Observation only
	Medical therapy
	Surgical intervention

Other complications: Bleeding into: Pericardium Pleura Peritoneum Retroperitoneum External hemorrhage Vessel perforation Cardiac arrest Arrhythmias including AV heart blocks Stroke Death Infection including suspected endocarditis and sepsis Post PDA ligation syndrome

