1.2 Study Design

This is a multi-center, single arm, non-randomized, observational study designed to help assure continued safety and effectiveness of FDA approved Amplatzer Piccolo Occluder device for PDA closure in premature infants less than 2 kg at the time of device implant. The study will be conducted at all the CCISC participating sites.

Subjects will have transcatheter PDA closure using the Amplatzer Piccolo Occluder device as part of standard clinical practice under fluoroscopy with or without additional echocardiographic image guidance. The study involves collecting and reporting of data for the ASO II AS PDA closure procedures into the CCISC PDA Module Database. The PDA module encompasses pre-procedure, procedure, 48-hoours, 1-month and 6-months post-procedure follow-up data entry. It also encompasses an adverse event reporting system. Data entry is expected for all attempted PDA closure procedures in which the Amplatzer Piccolo Occluder device is attempted in premature infants weighing < 2 kg at the time of the procedure. It includes pre-procedural and postprocedural echocardiographic information as well as data from procedural echo guidance if utilized. Follow-up will be for a period of six months +/- 30 days after the procedure.

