Effectiveness Endpoint: The effectiveness endpoint is the rate of effective closure of the PDA using a transcatheter device within six months post procedure. If more than one attempt is required, or multiple devices are required during the same procedure, it is still considered effective if there is Grade 0 or Grade 1 shunt, as defined below, at follow-up (within six months) by transthoracic echocardiography (TTE) or if a second procedure is not required following the initial attempt. If there is device embolization, adjacent vessel stenosis that required retrieval of the device and replacement during the same procedure with less than Grade 1 shunt during follow-up, it is still considered effective. Conversely, if an AE is noted after the procedure that requires a second procedure for treatment that results in greater than Grade 1 shunt, then the procedure is considered not effective, even if the initial attempt was effective.

PDA shunt definition:

Grade 0—none;

Grade 1—trivial (narrow jet adjacent to the device via the PDA). Note: the presence of flow via existing or newly formed aortopulmonary collaterals should not be considered as representing a shunt via the PDA. (See references in **Appendix B** by Skinner and Acherman)

Grade 2—mild (broader jet filling proximal left pulmonary artery branch and extending to main pulmonaryartery);

Grade 3/4—moderate to severe (wide jet filling the main pulmonary artery and extending to pulmonary valve or distal pulmonary artery branches, which also may be accompanied with the presence of flow reversal in the abdominal aortic Doppler pattern during diastole)

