7.2 Primary Effectiveness Endpoint

The primary effectiveness endpoint is the rate of effective closure of the PDA among subjects with a successful device implant as assessed by the presence of either a Grade 0 or Grade 1 shunt (see **Appendix A** for definition) at the 6 month follow-up visit by transthoracic echocardiography.

The proportions of subjects who have effective closure of the PDA at follow-up will be calculated along with the 95% confidence interval. The numerator for the event rate is the number of subjects who have effective closure of the PDA at follow-up. The denominator is the number of subjects in the analysis population (As detailed in Section 7.4). The primary effectiveness endpoint will be compared with the rate reported in the ADO II AS and Continued Access Protocol studies.

Among subjects successfully implanted with any device, the PDA occlusion rate is estimated to be approximately 99%.

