APPENDIX E: SCHEDULEOF ASSESSMENTS

	Pre- Catheterizatio	Device Implan	Follow up within 48 hours	Follow up at 30 ± 7 days	Follow up at 6 ± 1months
Domographia Data		шран	within 40110015	30 ± 7 uays	
Demographic Data	Х				
Physical Exam Data	Х		Х	Х	Х
Medical History					
Data	Х				
Procedure Data		Х			
Device Data		Х			
Transthoracic					
Echocardiogra					
m Data	Х	X *	Х	Х	Х
Adverse Event Data		Х	Х	Х	Х
Death Data		Х	Х	Х	Х
	* optional Intra-procedure Transthoracic Echocardiogram				

APPENDIXF

PROTOCOL DEVIATION REPORTING FORM

Report Date:	Title:	
Sponsor:	Principal Investigator:	
Date of Deviation/ Violation:	Subject Identifier: (if available)	

Reporting Deviations to IRB

*Sites must report violations that affect the safety and welfare of the subject to be submitted within 10 working days from the date the Investigator becomes aware of the event.

- Minor Deviations that do not affect the safety and welfare of the subject may be submitted at the time of continuing review. Please note that the sponsor's requirement may differ from IRB's reporting requirements; contact the sponsor and your institutional IRB to confirm if you have any questions regarding their policy.
- FDA 21 CFR 56.108(a)(4) and ICH 3.3.7 state that planned protocol deviations require prior approval of the IRB except when necessary to eliminate apparent immediate hazards to human subjects. Please submit this form to the CCISC as soon as possible after receiving sponsor approval for the planned deviation and prior to the deviation occurring.

Protocol Deviation/Violation Assessment		
Did the protocol deviation/violation affect the safe of the subject?	Yes* No	
Has the Sponsor been notified of this event?	Yes No	
Will the subject continue his/her participation in	Yes No	
Was the deviation planned or unplanned?	Planned**	Unplanned
(**please provide prior approval of Sponsor)		
Protocol Deviation/Violation Description and	Reason	

Please provide a description of the deviation/violation:

Please explain the reason for the	deviation/violation:	
-----------------------------------	----------------------	--

Corrective Action

Please describe what action(s) you have taken to prevent recurrence of this deviation/violation in the future:

Principal Investigator Signature:

Date:

Protocol Deviation Tracking Log

Tool:	Protocol Deviation Tracking Log				
Purpose:	To record all protocol deviations that occur at a study site				

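### Section 2.1 makes effectiveness depend on whether a second procedure is required, but the readable follow-up requirements contain no dedicated item to record one

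*Protocol*

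**What the plan says.** **Endpoint.** Protocol Section 2.1 frames effectiveness as closure by a transcatheter device within six months. A case is effective with a Grade 0 or 1 shunt at follow-up "or if a second procedure is not required following the initial attempt". It is not effective "if an AE is noted after the procedure that requires a second procedure for treatment that results in greater than Grade 1 shunt". Section 7.2 states the same endpoint without any second-procedure limb: effective closure is judged at 6 months "as assessed by the presence of either a Grade 0 or Grade 1 shunt".

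**Follow-up data.** Section 4.4 lists two blocks for the follow-up visits: "Demographics- including subject's age, weight", and a transthoracic echocardiogram. In Appendix E the row "Procedure Data" and the device row are marked at implant only. Adverse event and death data are marked at implant and at all three follow-up visits. No row is devoted to re-intervention.

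**Adverse event form.** Appendix D has structured outcomes for ligation or another device under embolization ("Successful transcatheter retrieval, PDA surgically ligated"), and for device exchange under left pulmonary artery and aortic stenosis ("Retrieval of device with use of a different device"). It also has an event type of Other.

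**Entry rule.** Section 1.2 expects module entry for "all attempted PDA closure procedures in which the Amplatzer Piccolo Occluder device is attempted in premature infants weighing < 2 kg".

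**The concern.** A duct that still shunts after a successful implant may later be ligated or given another device. That event is neither an embolization nor a stenosis, so the structured parts of Appendix D do not describe it, and no follow-up visit asks about it directly. Unless the site treats it as an adverse event, the record may show only a Grade 0/1 shunt at 6 months. The same record would arise if the first device had simply sealed late.

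What is at stake is whether the primary effectiveness rate describes the index device or the index device plus later procedures. Few failures are expected, so a handful of such cases could matter to the planned comparison with the earlier device studies. No later analysis can recover an event that was not collected.

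**Working it through.** The protocol gives no figure for re-intervention, so there is nothing to reproduce. The check sets the endpoint against the data collected, then shows the scale.

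**Step 1: when does second-procedure status decide the outcome?**

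| Shunt at 6 months | Second procedure | Section 2.1, read literally | Section 7.2 |
|---|---|---|---|
| Grade 0/1 | none | effective | effective |
| Grade 0/1 | performed | effective on the grade limb, but doubtful after ligation because the endpoint is framed as transcatheter closure | effective |
| above Grade 1 | not required | effective through the word *or* | not effective |
| above Grade 1 | required | not effective | not effective |

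Under Section 2.1, second-procedure status separates the last two rows. It also bears on the second row if a surgical closure is not to count as transcatheter. Under Section 7.2 it plays no part. The two sections disagree in the third row and may disagree in the second.

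**Step 2: where could a second procedure be recorded?**

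- Section 4.4 and the procedure and device rows of Appendix E: no follow-up entry.
- Appendix D, structured fields: only after embolization or stenosis.
- Appendix D, Other: possible, if the site files a form.
- Section 5.4: lists going back to remove a device, but not adding a device or ligating for residual shunt.
- Section 8.2: requires events that the investigator regards as potentially related, whatever their seriousness, and those of unknown relatedness. Residual shunt is not named as an adverse event in Sections 5.3 or 5.4, in the Appendix A examples or in Appendix D.
- Appendix G: free-text narrative, for serious events.
- A repeat module entry under Section 1.2: a further Piccolo attempt below 2 kg.

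The route that remains for a ligation or other device placed for residual shunt is discretionary. The *or* limb needs a negative, namely that no second procedure was required. The absence of an adverse event form cannot establish that.

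**Step 3: scale.** Inputs: 500 subjects (Section 2) and an expected occlusion rate of about 99% (Section 7.2). Assume that all 500 are evaluable and that every re-intervention counts as a failure. The number of missed cases k is not in the protocol, so a range is shown. Rate = (495 − k)/500, with exact binomial 95% intervals.

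| k | Effective | Rate | 95% CI |
|---|---|---|---|
| 0 | 495/500 | 99.0% | 97.68 to 99.67 |
| 1 | 494/500 | 98.8% | 97.41 to 99.56 |
| 5 | 490/500 | 98.0% | 96.35 to 99.04 |
| 10 | 485/500 | 97.0% | 95.10 to 98.31 |
| 15 | 480/500 | 96.0% | 93.89 to 97.54 |

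Each missed case moves the rate by 1/500 = 0.2 points. Expected failures number 500 × 0.01 = 5, so five missed cases would equal all of them. Section 7.4 excludes subjects without follow-up. With 400 evaluable, for example, each case moves the rate by 1/400 = 0.25 points.

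**The case against.** The strongest defense is that capture already exists. Adverse event data are scheduled at every visit, Appendix D has an Other type, Section 5.4 names a re-intervention, and Section 8.2 casts a wide net. Appendix A also counts events from inadequate implantation as adverse device effects, and a residual shunt needing treatment could be placed there. The failure clause in Section 2.1 is itself triggered by an adverse event, so adverse event reporting and the scheduled echocardiogram serve it. All of this stands. It leaves the case that the site does not regard as an adverse event.

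Four stronger readings are tempting, and the documents do not support them.

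- A reader might infer that no form can hold a later re-intervention. The routes above can hold one, and the follow-up page of the PDA module in Appendix C is incomplete in the text available: even the follow-up shunt grade is not visible. Absence of a field there is not shown.
- A reader might infer that the limb cannot be derived at all. Cases reported as adverse events can be classified.
- A reader might infer that the rate is biased upward. That follows only if re-intervention means failure. The literal *or* in Section 2.1 and the grade-only rule in Section 7.2 do not say so.
- A reader might infer that recording stops once an infant reaches 2 kg. Section 1.2 governs which closure procedures are entered. Follow-up and safety surveillance of an enrolled infant continue regardless.

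It is also fair that Section 7.6 sets no formal hypothesis, so no test result turns on this.

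**Conclusion.** The point holds as a gap in reliable capture. The readable follow-up requirements have no dedicated re-intervention item, and the structured adverse event outcomes cover re-closure, ligation and exchange only after embolization or stenosis. A further procedure for residual shunt that is not reported as an adverse event can be missed, and Section 7.2 would then credit the closure to the index procedure. The second-procedure limb of Section 2.1 cannot be reliably derived.

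The size is unknown. The figure of 0.2 points per case in 500 rests on three assumptions: all 500 evaluable, 99% apparent closure, and re-intervention scored as failure. The conclusion rests on Sections 2.1, 4.4 and 7.2 and Appendices D and E, which are readable, and not on Appendix C. It is a worthwhile, inexpensive correction and does not invalidate the design.

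**What to change.** 1. Add a re-intervention row to Appendix E at 48 hours, 30 days and 6 months, with a matching item in the PDA module (if the full follow-up page does not already have one): any further PDA procedure since the last visit, Yes/No. If Yes, record date, type, reason and the last shunt grade before it. Collect it for every enrolled subject, whatever the current weight and whether or not an adverse event form is filed.
2. Reconcile Sections 2.1 and 7.2 on whether closure by a second procedure counts as effective, and state one rule.
3. Report the effectiveness rate with and without subjects who had a second procedure.

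The cost is one schedule row and about five fields taken from the medical record. No new testing is needed, which fits the registry's reliance on standard practice. The reported effectiveness rate may come out somewhat lower.
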